#### **B. Statistical analysis**

For testing the study hypotheses, the following statistical methods will be used:

1. Descriptive statistics (mean and standard deviation) of the demographic data of all patients in both groups.
2. The suitable statistical tests will be used according to the nature of the collected data.
3. Level of significance for all tests will be set at  $p\text{-value} \leq 0.05$ .
4. The statistical package for social sciences (SPSS) version 26 for windows (Armonk, NY: IBM Corp) will be used for data statistical analysis.

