## **Delimitations**

This study will be delimited to:

- 30 children with spastic diplegia with age range from 6 to 12 years are enrolled in the study.
- Children will be randomly allocated into two equal groups; Group A will receive virtual reality and physiotherapy, while Group (B) will receive physiotherapy alone.
- All children will receive three sessions per week for twelve weeks.
- Variables will be evaluated pre and post treatment for all child.

- Gross motor performance will be evaluated using Gross Motor Function Measure 88 (GMFM-88).
- Balance will be evaluated using Pediatric Balance Scale (PBS).

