## **Hypotheses**

This study will test the following hypothesis:

There will be no significant the effects of virtual reality on gross motor performance and balance in children with spastic diplegia.

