#### **Sample size calculation:**

Using G-power version 3.1.9.7 for windows and regarding t-test study, alpha level of 0.05, confidence interval 80% and effect size of 1.135 calculated from the previous study of Krishna et al. (43), the total sample size will be 28 children (fourteen in each group), (Figure 1). We will increase number to be 30 children (Fifteen in each group) to avoid any drop out.

To avoid selection bias, the children will be randomly allocated by simple random method via choosing one of two wrapped cards representing the two treatment groups, which are:

- Group (A): will receive virtual reality in addition to the traditional exercise program.
- Group (B): will receive traditional exercise program.

[figure not shown]
[figure not shown]

Figure 1: Sample size calculation in G-power software program.

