**Figure 4: Neurodevelopmental approach**

**Figure 5: Approximation**

**Figure 6: Stretching exercise**

**Figure 7: Strengthening exercise**

**Figure 8: Spider suspension exercise**

**Figure 9: Gait training activities**

**Figure 10: Balance training program**

### **Data collection and statistical analysis:**

Data of all children in both groups will be collected and include:

1. Name, serial number and age (years).
2. gross motor performance pre- and post-treatment with GMFM 88.
3. balance pre and post treatment with PBS.

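### Two unranked outcomes share one null hypothesis and every test is at 0.05, with no primary outcome, between-group contrast or success rule fixed

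*Combined protocol and SAP*

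**What the plan says.** The Hypotheses section gives a single null that covers both domains: "There will be no significant the effects of virtual reality on gross motor performance and balance in children with spastic diplegia". Delimitations lists the two instruments side by side: "Gross motor performance will be evaluated using Gross Motor Function Measure 88 (GMFM-88") and "Balance will be evaluated using Pediatric Balance Scale (PBS"). Neither is called primary or secondary there, in Assessment instruments, in the data-collection list ("gross motor performance pre- and post-treatment with GMFM 88", then the same for PBS), or on the outcome sheet in Appendix VI.

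The inferential plan is two items in B. Statistical analysis. Item 2 reads "The suitable statistical tests will be used according to the nature of the collected data". Item 3 reads "Level of significance for all tests will be set at" p ≤ 0.05. That section refers to hypotheses in the plural, although only one is stated.

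The Sample size calculation uses a t-test, alpha 0.05, a figure of 80%, and an "effect size of 1.135 calculated from the previous study". It arrives at 28 children, 14 per group, and adds two: "We will increase number to be 30 children (Fifteen in each group) to avoid any drop out". It does not say which outcome or which contrast the 1.135 describes.

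**The concern.** A hypothesis that names two outcomes needs a rule for rejecting it, and the plan has none. Three readings are open: a significant result on either outcome rejects; both must be significant; or the outcomes are two separate questions. The contrast within each outcome is also open, because nothing says whether post-treatment scores, changes from baseline, or baseline-adjusted scores are compared.

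Both choices could be made once the data are in hand. At stake are the false-positive rate under the first reading, the power under the second, and the meaning of one significant and one non-significant result under the third. A reader also cannot tell which outcome the trial was sized for.

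**Working it through.** **Inputs.** From the Sample size calculation: d = 1.135, alpha 0.05, 14 per group planned, 15 per group enrolled. Two items are inferred. The 80% is labelled a confidence interval and is read here as power; the test is taken as two-sided. Not in the documents, so assumed and ranged: the correlation between GMFM-88 and PBS (0 to 0.9) and the pre–post correlation of a score. The simulations use normally distributed scores.

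**Step 1: reproduce the plan's sample size.** For a two-sample t-test with n per group, the noncentrality is d·√(n/2) on 2n − 2 degrees of freedom. At n = 14 this is 1.135 × √7 = 3.00 on 26 degrees of freedom. Two-sided power at 0.05:

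| n per group | Power |
|---|---|
| 13 | 79.3% |
| 14 | 82.4% |
| 15 | 85.1% |

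The smallest n reaching 80% is 14, so 28 children is reproduced exactly. A one-sided test would need 11 per group (22 children), which does not match. The trial is sized for one two-sided comparison.

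**Step 2: apply the three readings.** The planning case is 14 per group, since the two extra children are there to cover dropout. For independent outcomes, the chance of at least one false positive is 1 − 0.95² = 0.0975, and the power for both is about 0.824² = 0.679. Correlated cases come from simulation of bivariate normal scores, 400,000 replicates per cell, with d = 1.135 on both outcomes for power.

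| Correlation between outcomes | Either may reject: false-positive rate | Both required: power, n = 14 | Both required: power, n = 15 |
|---|---|---|---|
| 0 | 9.75% | 68% | 72% |
| 0.5 | 9.1% | 72% | 76% |
| 0.7 | 8.4% | 74% | 78% |
| 0.9 | 7.1% | 78% | 81% |

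Read as separate questions, each test has 5% error, but the single stated hypothesis has no decision rule.

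**Step 3: the open contrast.** Take one outcome, no treatment effect, 14 per group, and equal pre and post variances. Post-score, change-score and baseline-adjusted tests each have 5% error. If success is claimed when any of the three is significant, the error is 9.5%, 10.1% and 10.3% at pre–post correlations of 0.5, 0.7 and 0.9. Naming the outcome alone is therefore not enough.

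**Step 4: one named primary with a fixed contrast.**
- A t-test at 0.05 has 82.4% power at 14 per group if d = 1.135 applies to that outcome. The d that gives 80% power is 1.10 at 14 per group and 1.06 at 15.
- Baseline-adjusted (ANCOVA) power at 14 per group, 200,000 replicates, pre–post correlation 0, 0.3, 0.5, 0.7, 0.9: 80.7%, 84.3%, 90.4%, 97.6%, 100% if 1.135 is in units of the post-score SD; 97.9%, 93.8%, 90.3%, 86.4%, 82.7% if in units of the change-score SD. The minimum is about 81%.
- Testing the second outcome at 0.05 only after the first succeeds gives a simulated overall error of 5.0% when neither outcome has an effect.
- Bonferroni at 0.025 per outcome: per-outcome power 73.1% at 14, 76.6% at 15, 79.8% at 16 and 82.5% at 17. Reaching 80% takes 17 per group, or 34 children before dropout.

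**The case against.** The strongest reply is that inflation is not shown. Nothing in the plan says that either outcome may reject the hypothesis. The statistical section speaks of hypotheses in the plural, and the two domains are measured separately, so two questions at 5% each is a natural reading. This stands as far as it goes: the 7.1% to 9.75% applies only under the either-outcome reading. It does not supply the rule that the single stated hypothesis lacks, and it does not settle the contrast.

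Other points stand in part:
- The front pages and Figure 1 (the G-power output) are not in the text available for review. A primary outcome or the test type could appear there, so the finding is limited to what can be read.
- The 9.5% to 10.3% for the choice of contrast is a worst case, in which all three tests are run and any one counts. Item 2 of the statistical section may only mean parametric or non-parametric. Even so, the contrast is not stated.
- PBS is a bounded 0–56 sum of ordinal items and GMFM-88 a bounded percentage, so the normal-theory figures are approximate at this size.
- Declaring two separate hypotheses, each at 5%, would also close the gap in the rule with little rewording. It would still need the contrast fixed, and it would leave the trial without overall error control across its two claims.

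**Conclusion.** The concern holds on the text available. The plan's sample-size arithmetic is correct for one two-sided t-test, but the plan lists two outcomes and leaves both the rejection rule and the between-group contrast to be chosen later. The size depends on the reading: a false-positive rate of 7.1% to 9.75% if either outcome may reject; power of 68% to 78% at 14 per group if both are required; 5% per test, with no meaning assigned to a split result, if they are separate questions.

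These figures rest on assumed correlations of 0 to 0.9, on normal scores, and, for power, on d = 1.135 applying to both outcomes. The data remain usable, so this should be corrected before outcome data are analysed; it does not invalidate the design.

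**What to change.** Before any outcome data are analysed:

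1. In Hypotheses and B. Statistical analysis, name one total score, GMFM-88 or PBS, as the single primary outcome. Naming the total also settles that the five GMFM-88 dimension percentages are not tested as primary. If GMFM-88 is chosen, reconcile this with the provision under B. Assessment procedures that individual dimensions may be administered, so that every child has a total.
2. Fix the contrast as the post-treatment total score compared between groups with adjustment for the pre-treatment total score (ANCOVA), tested at two-sided 0.05. Both scores are already collected.
3. Test the other total score in the same way at 0.05 only if the primary is significant.
4. In the Sample size calculation, state which outcome and contrast 1.135 refers to, and tie the size to the named primary. If 1.135 does not apply to that primary, state the effect size assumed for it and restate the power; 14 per group gives 80% t-test power only for d of 1.10 or more.

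The cost is wording in three sections. No extra children are needed if 1.135 applies to the named primary (82% power for a t-test at 14 per group, at least 81% for the adjusted comparison); otherwise the sample size has to be re-checked. The downside is that the second outcome can be claimed only after the first. With unadjusted t-tests, the chance of claiming both is 68% to 78% at 14 per group if d = 1.135 holds for both.

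If the sponsor wants either outcome to count, Bonferroni at 0.025 each is the costlier alternative: 73% power per outcome at 14 per group, 77% at 15, and 34 children before dropout to reach 80%.

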# APPENDICES

## Appendix I

### Modified Ashworth Scale

# MODIFIED ASHWORTH SCALE

| Score | Ashworth Scale (1964)                         | Modified Ashworth Scale Bohannon & Smith (1987)  |
|-------|---|--|
| 0 (0) | No increase in tone                           | No increase in muscle tone   |
| 1 (1) | Slight increase in tone catch when limb moved | Slight increase in muscle tone, manifested by a catch and release or by minimal resistance at the end of the range of motion when the affected part(s) is moved in flexion or extension. |
| 1+(2) |   | Slight increase in muscle tone, manifested by a catch, followed by minimal resistance throughout the remainder (less than half) of the ROM (range of movement).                          |
| 2 (3) | marked increase in tone limb easily flexed    | More marked increase in muscle tone through most of the ROM, but affected part(s) easily moved.  |
| 3 (4) | passive movement difficult                    | Considerable increase in muscle tone passive, movement difficult.  |
| 4 (5) | Limb rigid                                    | Affected part(s) rigid in flexion or extension.  |

## Appendix II

### GROSS MOTOR FUNCTION MEASURE (GMFM) SCORE SHEET (GMFM-88 and GMFM-66 scoring)

Child's Name: \_\_\_\_\_ ID#: \_\_\_\_\_

Assessment Date: \_\_\_\_\_ GMFCS Level:  
year / month / day  I  II  III  IV  V

Date of Birth: \_\_\_\_\_  
year / month / day

Chronological Age: \_\_\_\_\_ Evaluator's Name: \_\_\_\_\_  
year / month / day

Testing Condition (e.g., room, clothing, time, others present): \_\_\_\_\_

The GMFM is a standardized observational instrument designed and validated to measure change in gross motor function over time in children with cerebral palsy. The scoring key is meant to be a general guideline. However, most of the items have specific descriptors for each score. It is imperative that the guidelines contained in the manual be used for scoring each item.

| SCORING KEY        |  |
|--------------------|--|
| 0                  | = does not initiate                              |
| 1                  | = initiates                                      |
| 2                  | = partially completes                            |
| 3                  | = completes                                      |
| 9 (or leave blank) | = not tested (NT) [used for the GMAE-2 scoring*] |

**It is important to differentiate a true score of "0" (child does not initiate) from an item which is Not Tested (NT) if you are interested in using the GMFM-66 Ability Estimator (GMAE) Software.**

The most accurate version of the GMFM-66 scoring program is the GMAE-3. It is included in the GMFM App+ which is available from the CanChild shop (<https://www.canchild.ca/en/shop>). The GMAE-2 is available at [www.canchild.ca](http://www.canchild.ca) but is incompatible with newer computer operating systems. The GMFM-66 is only valid for use with children who have cerebral palsy tested without shoes, orthoses, or aides.

#### Contact for Research Group:

CanChild Centre for Childhood Disability Research,  
Institute for Applied Health Sciences, McMaster University,  
[name],  
[name]  
Email: [[contact]](mailto:[contact]) Website: [www.canchild.ca](http://www.canchild.ca)

GMFCS level is a rating of severity of motor function. Definitions for the GMFCS-E&R (expanded & revised) are found in Palisano et al. (2008). *Developmental Medicine & Child Neurology*. 50:744-750 and in the GMAE-3 scoring software. <http://motorgrowth.canchild.ca/en/GMFCS/resources/GMFCS-ER.pdf>

Check (3) the appropriate score: if an item is not tested (NT), circle the item number on the right column

| Item                     | A: LYING & ROLLING  | SCORE                      |                            |                            |                            | NT  |
|--------------------------|---|----------------------------|----------------------------|----------------------------|----------------------------|-----|
| 1.                       | SUP, HEAD IN MIDLINE: TURNS HEAD WITH EXTREMITIES SYMMETRICAL .....           | 0  | 1  | 2  | 3  | 1.  |
| * 2.                     | SUP: BRINGS HANDS TO MIDLINE, FINGERS ONE WITH THE OTHER.....                 | 0  | 1  | 2  | 3  | 2.  |
| 3.                       | SUP: LIFTS HEAD 45° .....   | 0  | 1  | 2  | 3  | 3.  |
| 4.                       | SUP: FLEXES R HIP & KNEE THROUGH FULL RANGE .....                             | 0  | 1  | 2  | 3  | 4.  |
| 5.                       | SUP: FLEXES L HIP & KNEE THROUGH FULL RANGE.....                              | 0  | 1  | 2  | 3  | 5.  |
| * 6.                     | SUP: REACHES OUT WITH R ARM, HAND CROSSES MIDLINE TOWARD TOY.....             | 0  | 1  | 2  | 3  | 6.  |
| * 7.                     | SUP: REACHES OUT WITH L ARM, HAND CROSSES MIDLINE TOWARD TOY .....            | 0  | 1  | 2  | 3  | 7.  |
| 8.                       | SUP: ROLLS TO PR OVER R SIDE .....  | 0  | 1  | 2  | 3  | 8.  |
| 9.                       | SUP: ROLLS TO PR OVER L SIDE .....  | 0  | 1  | 2  | 3  | 9.  |
| * 10.                    | PR: LIFTS HEAD UPRIGHT.....   | 0  | 1  | 2  | 3  | 10. |
| 11.                      | PR ON FOREARMS: LIFTS HEAD UPRIGHT, ELBOWS EXT., CHEST RAISED.....            | 0  | 1  | 2  | 3  | 11. |
| 12.                      | PR ON FOREARMS: WEIGHT ON R FOREARM, FULLY EXTENDS OPPOSITE ARM FORWARD.....  | 0  | 1  | 2  | 3  | 12. |
| 13.                      | PR ON FOREARMS: WEIGHT ON L FOREARM, FULLY EXTENDS OPPOSITE ARM FORWARD ..... | 0  | 1  | 2  | 3  | 13. |
| 14.                      | PR: ROLLS TO SUP OVER R SIDE.....   | 0  | 1  | 2  | 3  | 14. |
| 15.                      | PR: ROLLS TO SUP OVER L SIDE .....  | 0  | 1  | 2  | 3  | 15. |
| 16.                      | PR: PIVOTS TO R 90° USING EXTREMITIES .....                                   | 0  | 1  | 2  | 3  | 16. |
| 17.                      | PR: PIVOTS TO L 90° USING EXTREMITIES.....                                    | 0  | 1  | 2  | 3  | 17. |
| TOTAL DIMENSION A |   |                            |                            |                            |                            |     |

| Item                     | B: SITTING   | SCORE                      |                            |                            |                            | NT  |
|--------------------------|--|----------------------------|----------------------------|----------------------------|----------------------------|-----|
| * 18.                    | SUP, HANDS GRASPED BY EXAMINER: PULLS SELF TO SITTING WITH HEAD CONTROL.....                         | 0  | 1  | 2  | 3  | 18. |
| 19.                      | SUP: ROLLS TO R SIDE, ATTAINS SITTING .....  | 0  | 1  | 2  | 3  | 19. |
| 20.                      | SUP: ROLLS TO L SIDE, ATTAINS SITTING .....  | 0  | 1  | 2  | 3  | 20. |
| * 21.                    | SIT ON MAT, SUPPORTED AT THORAX BY THERAPIST: LIFTS HEAD UPRIGHT, MAINTAINS 3 SECONDS .....          | 0  | 1  | 2  | 3  | 21. |
| * 22.                    | SIT ON MAT, SUPPORTED AT THORAX BY THERAPIST: LIFTS HEAD MIDLINE, MAINTAINS 10 SECONDS .....         | 0  | 1  | 2  | 3  | 22. |
| * 23.                    | SIT ON MAT, ARM(S) PROPPING: MAINTAINS, 5 SECONDS .....  | 0  | 1  | 2  | 3  | 23. |
| * 24.                    | SIT ON MAT: MAINTAIN, ARMS FREE, 3 SECONDS .....   | 0  | 1  | 2  | 3  | 24. |
| * 25.                    | SIT ON MAT WITH SMALL TOY IN FRONT: LEANS FORWARD, TOUCHES TOY, RE-ERECTS WITHOUT ARM PROPPING ..... | 0  | 1  | 2  | 3  | 25. |
| * 26.                    | SIT ON MAT: TOUCHES TOY PLACED 45° BEHIND CHILD'S R SIDE, RETURNS TO START .....                     | 0  | 1  | 2  | 3  | 26. |
| * 27.                    | SIT ON MAT: TOUCHES TOY PLACED 45° BEHIND CHILD'S L SIDE, RETURNS TO START.....                      | 0  | 1  | 2  | 3  | 27. |
| 28.                      | R SIDE SIT: MAINTAINS, ARMS FREE, 5 SECONDS .....  | 0  | 1  | 2  | 3  | 28. |
| 29.                      | L SIDE SIT: MAINTAINS, ARMS FREE, 5 SECONDS .....  | 0  | 1  | 2  | 3  | 29. |
| * 30.                    | SIT ON MAT: LOWERS TO PR WITH CONTROL .....  | 0  | 1  | 2  | 3  | 30. |
| * 31.                    | SIT ON MAT WITH FEET IN FRONT: ATTAINS 4 POINT OVER R SIDE.....                                      | 0  | 1  | 2  | 3  | 31. |
| * 32.                    | SIT ON MAT WITH FEET IN FRONT: ATTAINS 4 POINT OVER L SIDE.....                                      | 0  | 1  | 2  | 3  | 32. |
| 33.                      | SIT ON MAT: PIVOTS 90°, WITHOUT ARMS ASSISTING.....  | 0  | 1  | 2  | 3  | 33. |
| * 34.                    | SIT ON BENCH: MAINTAINS, ARMS AND FEET FREE, 10 SECONDS.....   | 0  | 1  | 2  | 3  | 34. |
| * 35.                    | STD: ATTAINS SIT ON SMALL BENCH .....  | 0  | 1  | 2  | 3  | 35. |
| * 36.                    | ON THE FLOOR: ATTAINS SIT ON SMALL BENCH .....   | 0  | 1  | 2  | 3  | 36. |
| * 37.                    | ON THE FLOOR: ATTAINS SIT ON LARGE BENCH .....   | 0  | 1  | 2  | 3  | 37. |
| TOTAL DIMENSION B |  |                            |                            |                            |                            |     |

| Item  | C: CRAWLING & KNEELING  | SCORE                      |                            |                            |                            | NT  |
|-------|---|----------------------------|----------------------------|----------------------------|----------------------------|-----|
| 38.   | PR: CREEPS FORWARD 1.8m (6') .....  | 0  | 1  | 2  | 3  | 38. |
| * 39. | 4 POINT: MAINTAINS, WEIGHT ON HANDS AND KNEES, 10 SECONDS .....                       | 0  | 1  | 2  | 3  | 39. |
| * 40. | 4 POINT: ATTAINS SIT ARMS FREE .....  | 0  | 1  | 2  | 3  | 40. |
| * 41. | PR: ATTAINS 4 POINT, WEIGHT ON HANDS AND KNEES .....                                  | 0  | 1  | 2  | 3  | 41. |
| * 42. | 4 POINT: REACHES FORWARD WITH R ARM, HAND ABOVE SHOULDER LEVEL .....                  | 0  | 1  | 2  | 3  | 42. |
| * 43. | 4 POINT: REACHES FORWARD WITH L ARM, HAND ABOVE SHOULDER LEVEL .....                  | 0  | 1  | 2  | 3  | 43. |
| * 44. | 4 POINT: CRAWLS OR HITCHES FORWARD 1.8m(6') .....                                     | 0  | 1  | 2  | 3  | 44. |
| * 45. | 4 POINT: CRAWLS RECIPROCALLY FORWARD 1.8m ( 6') .....                                 | 0  | 1  | 2  | 3  | 45. |
| * 46. | 4 POINT: CRAWLS UP 4 STEPS ON HANDS AND KNEES/FEET .....                              | 0  | 1  | 2  | 3  | 46. |
| 47.   | 4 POINT: CRAWLS BACKWARDS DOWN 4 STEPS ON HANDS AND KNEES/FEET .....                  | 0  | 1  | 2  | 3  | 47. |
| * 48. | SIT ON MAT: ATTAINS HIGH KN USING ARMS, MAINTAINS, ARMS FREE, 10 SECONDS .....        | 0  | 1  | 2  | 3  | 48. |
| 49.   | HIGH KN: ATTAINS HALF KN ON R KNEE USING ARMS, MAINTAINS, ARMS FREE, 10 SECONDS ..... | 0  | 1  | 2  | 3  | 49. |
| 50.   | HIGH KN: ATTAINS HALF KN ON L KNEE USING ARMS, MAINTAINS, ARMS FREE, 10 SECONDS ..... | 0  | 1  | 2  | 3  | 50. |
| * 51. | HIGH KN: KN WALKS FORWARD 10 STEPS, ARMS FREE .....                                   | 0  | 1  | 2  | 3  | 51. |

TOTAL DIMENSION C

| Item  | D: STANDING   | SCORE                      |                            |                            |                            | NT  |
|-------|---|----------------------------|----------------------------|----------------------------|----------------------------|-----|
| * 52. | ON THE FLOOR: PULLS TO STD AT LARGE BENCH .....                             | 0  | 1  | 2  | 3  | 52. |
| * 53. | STD: MAINTAINS, ARMS FREE, 3 SECONDS .....                                  | 0  | 1  | 2  | 3  | 53. |
| * 54. | STD: HOLDING ON TO LARGE BENCH WITH ONE HAND, LIFTS R FOOT, 3 SECONDS ..... | 0  | 1  | 2  | 3  | 54. |
| * 55. | STD: HOLDING ON TO LARGE BENCH WITH ONE HAND, LIFTS L FOOT, 3 SECONDS ..... | 0  | 1  | 2  | 3  | 55. |
| * 56. | STD: MAINTAINS, ARMS FREE, 20 SECONDS .....                                 | 0  | 1  | 2  | 3  | 56. |
| * 57. | STD: LIFTS L FOOT, ARMS FREE, 10 SECONDS .....                              | 0  | 1  | 2  | 3  | 57. |
| * 58. | STD: LIFTS R FOOT, ARMS FREE, 10 SECONDS .....                              | 0  | 1  | 2  | 3  | 58. |
| * 59. | SIT ON SMALL BENCH: ATTAINS STD WITHOUT USING ARMS .....                    | 0  | 1  | 2  | 3  | 59. |
| * 60. | HIGH KN: ATTAINS STD THROUGH HALF KN ON R KNEE, WITHOUT USING ARMS .....    | 0  | 1  | 2  | 3  | 60. |
| * 61. | HIGH KN: ATTAINS STD THROUGH HALF KN ON L KNEE, WITHOUT USING ARMS .....    | 0  | 1  | 2  | 3  | 61. |
| * 62. | STD: LOWERS TO SIT ON FLOOR WITH CONTROL, ARMS FREE .....                   | 0  | 1  | 2  | 3  | 62. |
| * 63. | STD: ATTAINS SQUAT, ARMS FREE .....   | 0  | 1  | 2  | 3  | 63. |
| * 64. | STD: PICKS UP OBJECT FROM FLOOR, ARMS FREE, RETURNS TO STAND .....          | 0  | 1  | 2  | 3  | 64. |

TOTAL DIMENSION D

| Item  | E: WALKING, RUNNING & JUMPING  | SCORE                      |                            |                            |                            | NT  |
|-------|--|----------------------------|----------------------------|----------------------------|----------------------------|-----|
| * 65. | STD, 2 HANDS ON LARGE BENCH: CRUISES 5 STEPS TO R .....                              | 0  | 1  | 2  | 3  | 65. |
| * 66. | STD, 2 HANDS ON LARGE BENCH: CRUISES 5 STEPS TO L .....                              | 0  | 1  | 2  | 3  | 66. |
| * 67. | STD, 2 HANDS HELD: WALKS FORWARD 10 STEPS .....                                      | 0  | 1  | 2  | 3  | 67. |
| * 68. | STD, 1 HAND HELD: WALKS FORWARD 10 STEPS .....                                       | 0  | 1  | 2  | 3  | 68. |
| * 69. | STD: WALKS FORWARD 10 STEPS .....  | 0  | 1  | 2  | 3  | 69. |
| * 70. | STD: WALKS FORWARD 10 STEPS, STOPS, TURNS 180°, RETURNS .....                        | 0  | 1  | 2  | 3  | 70. |
| * 71. | STD: WALKS BACKWARD 10 STEPS .....   | 0  | 1  | 2  | 3  | 71. |
| * 72. | STD: WALKS FORWARD 10 STEPS, CARRYING A LARGE OBJECT WITH 2 HANDS .....              | 0  | 1  | 2  | 3  | 72. |
| * 73. | STD: WALKS FORWARD 10 CONSECUTIVE STEPS BETWEEN PARALLEL LINES 20cm (8") APART ..... | 0  | 1  | 2  | 3  | 73. |
| * 74. | STD: WALKS FORWARD 10 CONSECUTIVE STEPS ON A STRAIGHT LINE 2cm (3/4") WIDE .....     | 0  | 1  | 2  | 3  | 74. |
| * 75. | STD: STEPS OVER STICK AT KNEE LEVEL, R FOOT LEADING .....                            | 0  | 1  | 2  | 3  | 75. |
| * 76. | STD: STEPS OVER STICK AT KNEE LEVEL, L FOOT LEADING .....                            | 0  | 1  | 2  | 3  | 76. |
| * 77. | STD: RUNS 4.5m (15'), STOPS & RETURNS .....  | 0  | 1  | 2  | 3  | 77. |
| * 78. | STD: KICKS BALL WITH R FOOT .....  | 0  | 1  | 2  | 3  | 78. |
| * 79. | STD: KICKS BALL WITH L FOOT .....  | 0  | 1  | 2  | 3  | 79. |
| * 80. | STD: JUMPS 30cm (12") HIGH, BOTH FEET SIMULTANEOUSLY .....                           | 0  | 1  | 2  | 3  | 80. |
| * 81. | STD: JUMPS FORWARD 30 cm (12"), BOTH FEET SIMULTANEOUSLY .....                       | 0  | 1  | 2  | 3  | 81. |
| * 82. | STD ON R FOOT: HOPS ON R FOOT 10 TIMES WITHIN A 60cm (24") CIRCLE .....              | 0  | 1  | 2  | 3  | 82. |
| * 83. | STD ON L FOOT: HOPS ON L FOOT 10 TIMES WITHIN A 60cm (24") CIRCLE .....              | 0  | 1  | 2  | 3  | 83. |
| * 84. | STD, HOLDING 1 RAIL: WALKS UP 4 STEPS, HOLDING 1 RAIL, ALTERNATING FEET .....        | 0  | 1  | 2  | 3  | 84. |
| * 85. | STD, HOLDING 1 RAIL: WALKS DOWN 4 STEPS, HOLDING 1 RAIL, ALTERNATING FEET .....      | 0  | 1  | 2  | 3  | 85. |
| * 86. | STD: WALKS UP 4 STEPS, ALTERNATING FEET .....  | 0  | 1  | 2  | 3  | 86. |
| * 87. | STD: WALKS DOWN 4 STEPS, ALTERNATING FEET .....                                      | 0  | 1  | 2  | 3  | 87. |
| * 88. | STD ON 15cm (6") STEP: JUMPS OFF, BOTH FEET SIMULTANEOUSLY .....                     | 0  | 1  | 2  | 3  | 88. |

TOTAL DIMENSION E

Was this assessment indicative of this child's "regular" performance? YES  NO

COMMENTS:

---

---

---

---

---

---

---

---

---

---

